9.2 DEFINITION OF SERIOUS ADVERSE EVENT (SAE)

An adverse event is considered "serious" if, in the view of either the investigator or sponsor, it results in any of the following outcomes:

- Death;
- A life-threatening adverse event;
- Inpatient hospitalization or prolongation of existing hospitalization;
- A persistent or significant incapacity or substantial disruption of the ability to conduct normal life functions;
- Congenital anomaly/ birth defect;
- An important medical event that may not result in death, be life-threatening, or require hospitalization may be considered serious when, based upon appropriate medical judgment, they may jeopardize the patient or subject and may require medical or surgical intervention to prevent one of the outcomes listed in this definition. Examples of such medical events include allergic bronchospasm requiring intensive treatment in an emergency room or at home, blood dyscrasias or convulsions that do not result in inpatient hospitalization, or the development of drug dependency or drug abuse.

Note that seriousness and severity should not be confused. A subject could experience a severe headache that would not qualify as an SAE, while another might experience a mild stroke that, while not severe, would be considered serious.

9.3 RECORDING OF ADVERSE EVENTS

All untoward events occurring between visit 1 (week 0) (post-injection) and the end of study (or if subject terminates from study prior to visit 34 (week 36), five weeks after the last administration of bermekimab) should be recorded on the eCRF, regardless of whether they are considered related to study drug.

All AEs should be recorded in a standard medical terminology as concisely as possible. The AE recorded should not be a procedure or a clinical/laboratory measurement but should reflect the event leading to the

procedure or the cause of the clinical/laboratory abnormality, if known. Whenever possible, AEs should be evaluated and recorded as a diagnosis, rather than individual signs and symptoms. However, if a definitive diagnosis is not possible, the individual signs and symptoms should be recorded. Any AE that worsens in intensity, or becomes serious, should be recorded as a new event.

9.4 EVALUATING ADVERSE EVENTS

All AEs will be graded according to the CTCAE version 5.

9.5 ASSESSMENT OF CAUSALITY

Investigators are required to assess the relationship, if any, of each AE or SAE to the investigational drug using clinical judgment to determine the degree of certainty with which an AE can be attributed to the investigational drug. Alternative causes, such as natural history of the underlying disease, other risk factors, and the temporal relationship of the event to the administration of the study medication must be considered.

Relationship to study drug is summarized as follows:

- Not Related: There is another obvious cause of the AE
- Unlikely to be related: There is another more likely cause of the AE
- **Possibly related:** The AE could have been due to the investigational drug
- **Probably related:** The AE is probably attributable to the investigational drug
- **Definitely related:** The AE is most likely attributable to the investigational drug

9.6 REPORTING REQUIREMENTS

Any grade 3 or greater adverse event and injection site reaction must be reported to the sponsor within 24 hours of learning of the event.

All serious adverse events (SAEs) should be reported to the Sponsor on the initial SAE report forms within 24 hours of knowledge of the event. These immediate reports should be followed promptly by detailed, written reports (follow-up SAE reports). The subject should be followed up with until stabilization of the reported SAE, either with full satisfactory resolution or resolution with sequelae, or until death of the subject. Before declaring the subject is lost to follow-up, three unsuccessful attempts at contact should be made and recorded on the SAE form. The immediate and follow-up reports should identify subjects by unique code numbers (generated by the safety database) assigned to the trial subjects rather than by the subjects' names, personal identification numbers, and/or addresses. The Investigator should also submit

SAEs to the IRB/EC according to their IRB/EC guidelines [ICH-GCP E6]. Drug-related Serious Adverse Events will be reported to the FDA by XBiotech's Medical Safety Officer according to 21 CFR 312.32.

9.7 REFERENCE SAFETY INFORMATION: POTENTIAL ADVERSE REACTIONS

More than 900 patients have been treated using bermekimab (either by infusions or subcutaneous injections) in patients with advanced solid tumors, advanced hematologic malignancies, metastatic colorectal cancer, peripheral vascular disease, type II diabetes, acne vulgaris, plaque psoriasis, pyoderma gangrenosum, atopic dermatitis and hidradenitis suppurativa. Repeat dose toxicity in relevant species, safety pharmacology, genotoxicity, carcinogenic potential, and toxicity to reproduction studies have not been performed. A repeat dose toxicity study in mice did not reveal any unspecific toxicity related to bermekimab. Over 5000 doses of bermekimab were administered intravenously (50 mg/mL) at 7.5 mg/kg and over 900 doses of bermekimab were administered subcutaneously with 100 mg/mL and 200 mg/ mL formulations.

Bermekimab is a recombinant human IgG1 monoclonal antibody specific for human interleukin-1 α (IL-1 α). As such, it is an immunomodulator that has anti-inflammatory and anti-neoplastic properties. Other agents that could be considered in the same pharmacologic class include biologic agents that target IL-1 receptor antagonist and IL-1 beta. Potential risks for agents in this class include infusion or injection site reactions and risk of infection.

Bermekimab is True Human monoclonal antibody derived immune plasma B cells derived from a natural human immune response against IL-1 α . Unlike previous generations of humanized or fully human antibodies, the entire bermekimab heavy and light chain sequences are identical to those found in naturally-occurring human IgG1 κ , with the light and heavy chain variable regions being identical to those originally expressed by a peripheral blood B lymphocyte that was obtained from a healthy individual. No *in vitro* affinity maturation or modifications have been made to improve its natural binding affinity (211 +/- 31 pM). We believe that a true human antibody should be effectively non-immunogenic in humans and thus exhibit optimal activity and pharmacokinetics. To date, no treatment emergent anti-drug antibodies specific to bermekimab have been identified.

The mechanism behind infusion or injection site reactions is not well understood. In some cases, it may involve a reaction against the antibody products themselves, particularly where the primary sequence of the antibody has been modified in vitro or is derived from non-human system or, against some minor residual component from the manufacturing process (i.e. host cell proteins). Bermekimab is derived from and has undergone immunological selection in humans, thus anti-bermekimab responses are highly unlikely. To date, there has been a very low incidence of injection site or infusion reactions observed (27 patients out of 911 total; 3.0%). In order to mitigate this class-specific risk, close monitoring is required during the bermekimab infusion/ injection and for at least 30 minutes after the end of the infusion/ injection for the first 3 doses. Availability of resuscitation equipment must be ensured although this has never been used for any patient in any of our studies. Pre-medication with antihistamines, NSAIDs or corticosteroids is not required but allowed at PI's discretion.

For the purposes of expedited safety reporting in clinical trials, the following should be considered expected events:

- Infusion Related Reactions
- Injection Site Reactions

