3. STUDY DESIGN AND OBJECTIVES

This is a randomized, double-blind, placebo-controlled study to further establish the efficacy and safety and explore dose effects for bermekimab monotherapy in adults with moderate-to-severe HS. Approximately 50% of patients enrolled will have failed prior targeted biologic therapy(ies) and approximately 50% will be naïve to these forms of biologic therapy in each arm. Patients will be assessed for study eligibility at the initial screening visit after providing informed consent. Thirty days are allowed in the screening window to complete all screening procedures and randomize the subject. During the screening period, certain treatments will be washed out, as applicable, according to eligibility requirements. Patients who fail initially may be re-screened once based on the investigator discretion but only if inclusion criteria are met at time of rescreening.

The study is approximately 40 weeks (30 day screening period, 32-week treatment period and a 4-week follow-up period) for all subjects.

Patients who meet eligibility criteria at screening will be randomized in a 1:1:1 fashion to one of three treatment arms:

- Arm 1: 800 mg loading dose of bermekimab (2 x 400 mg SC injections) at weeks 0 and 1 followed by weekly (qw) subcutaneous (SC) injections of 400 mg bermekimab through week 31
- Arm 2: 800 mg loading dose of bermekimab (2 x 400 mg SC injections) at weeks 0 and 1 followed by subcutaneous (SC) injections of 400 mg bermekimab every other week (q2w) alternating with matching placebo q2w through week 31.
- Arm 3: 4mL loading dose of placebo (2 x 2mL SC injections) at weeks 0 and 1 followed by weekly placebo injections from weeks 2 through week 15. Patients in Arm 3 will begin to receive weekly (qw) blinded subcutaneous (SC) injections of 400 mg bermekimab beginning at week 16 through week 31.

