5. TREATMENT PLAN

5.1 STUDY PROCEDURES

PLACEBO-CONTROLLED PERIOD

Screening (maximum 30 days): The screening period begins once the informed consent is signed.

- Informed Consent
- Inclusion/ Exclusion
- Medical History/ Demographics
- Height, Weight, Body Mass Index (BMI) [BMI= weight (kg)/height (m2)]
- Concomitant Medications/treatments
- Provide subject copies of the patient take home diary, which will consist of NRS pain (worst moment, average & current) and itch (worst moment & average) assessments to be completed by patients daily.
- Lesion Counts (HiSCR), mHSS, HS-PGA, PGA-ISD, IHS4, Hurley Staging
- DLQI, HADS, PGI-c, PGI-s, EQ-5D-3L, HSSD, HiSQOL
- Physical Exam
- Electrocardiogram
- Vital Signs (blood pressure, pulse, oxygen saturation, respiratory rate and body temperature)
- Urinalysis: pH, protein, glucose and blood cells (RBCs and WBCs)
- Blood Draw:
 - o Chemistry panel: Albumin, Alkaline Phosphatase, ALT, AST, GGT,

Bicarbonate (CO2), Calcium, Chloride, Creatinine, Glucose, Potassium, Sodium, Total Bilirubin, Total Protein, Urea Nitrogen (BUN)

- Hematology Panel: Complete Blood Count (CBC) with differential and platelets
- Infectious disease panel: HIV antibody, Hepatitis C antibody, Hepatitis B panel (HBsAg, anti-HBc, anti-HBs), and interferon gamma release assay (IGRA) for TB
- Serum pregnancy test for WOCBP
- Inflammation Markers: CRP (C-Reactive Protein), ESR (Erythrocyte Sedimentation Rate)
- Randomization to study arm (once confirmed patient has passed screening requirements).

***Patients will be monitored at the study site at visits 1, 2, 3, 17, 18 & 19 (weeks 0, 1, 2, 16, 17 & 18) for a minimum of 30-minutes after study drug administration. Vital signs and AE assessments will be done at 30 minutes (+/- 10 minutes) post-injection. ***

Visit 1 (Week 0) (day 0, must occur within 30 days of signing informed consent):

- At least 45 minutes before injection: Remove syringe from refrigeration and lay flat; allow to warm to room temperature. Do not heat
- Pre-injection
 - Verify patient still meets inclusion/exclusion criteria
 - Height, Weight, Body Mass Index (BMI) [BMI= weight (kg)/height (m2)]
 - Patient Diary
 - Baseline Lesion Counts (for future HiSCR assessments), mHSS, HS-PGA, PGA-ISD, IHS4 and Hurley Staging
 - o DLQI, HADS, PGI-c, PGI-s, EQ-5D-3L, HSSD, HiSQOL
 - Physical Exam, Vital signs, Urine pregnancy
 - o Urinalysis
 - Blood draw for chemistry, hematology, inflammation markers, PK/ADA, IL-6,

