5.2 STUDY CALENDARS

5.2.1 Placebo-controlled Period

Study Procedure	Screening	Baseline Placebo-controlled Period																
Visit (V)		V1	V2	V3	V4	V5	V6	V 7	V8	V9	V10	V11	V12	V13	V14	V15	V16	V17
Week (W)		W0	W1	W2	W3	W4	W5	W6	W 7	W8	W9	W10	W11	W12	W13	W14	W15	W16
Day (D)	-30 to -1	D 0	D 7	D14	D21	D28	D35	D42	D49	D56	D63	D 70	D 77	D84	D91	D98	D105	D112
Visit Window (d)	+5d	±3d	±3d	±3d	±3d	±3d	±3d	±3d	±3d	±3d	±3d	±3d	±3d	±3d	±3d	±3d	±3d	±3d
Screening/Baseline: ¹	•	•		•	•	•				•			•				•	
Informed Consent	X																	
Inclusion/Exclusion	Х	Х																
Medical History/ Demographics	Х																	
Height, Weight, BMI	Х	Х																
Randomization	Х																	
Treatment: ^{2, 3, 5}		•				•							•					
Administer Study Drug		X ⁶	X ⁶	X	Х	X	X	X	X	X	X	X	X	X	X	X	Х	X ⁷
Con Meds/ Treatments	X	Х	X	Х	Х	Х	Х	Х	Х	Х	X	Х	Х	X	Х	Х	Х	Х
Efficacy: ⁴																		
Patient Diary (daily)	X	X	X	X	X	X	x	x	X	X	x	x	X	x	x	x	X	X
HiSCR, mHSS, HS PGA, PGA-ISD,																		
IHSER, IIIISS, IIS FOR, FOR ISD, IHS4	X	X	X		X		X		X		X			X				X
Hurley Stage	X	X	X		X		X		X		X			X				X
DLQI, HADS, PGI-C, PGI-S, EQ-5D-																		
3L, HSSD, HiSQOL	X	X	Х		X		X		X		X			X				X
Safety: ⁴	1	•				•							•					
Physical Examination	X	X	X		Х		X		X		X		X	X				X
Electrocardiogram	Х																	
Vital Signs	Х	Х	X	Х	Х	Х	Х	Х	Х	Х	Х	Х	Х	Х	Х	Х	Х	Х
Adverse Events		Х	X	Х	Х	Х	Х	Х	Х	Х	Х	Х	Х	Х	Х	Х	Х	Х
Laboratory Testing: ⁴																		
Infectious Disease Panel	X																	
Hematology, Chemistry, Inflammation																		
Markers	X	X								X				X				X
Urinalysis	X	Х								Х								X
Pregnancy Test (WOCBP only)	Serum	X	X	X	X	X	X	X	X	X	x	X	X	x	X	X	X	X
PK/PD/ADA: ⁴																		
PK/ADA, IL-6, PD, biomarker &																		
research samples (serum/plasma)		X	X	X	X	X	X			X				X				X
/	¹ 30 days are allowed to complete all screening procedures and randomization.																	
² Patients will be monitored at the study site at visits 1, 2, 3, 17, 18 & 19 (weeks 0, 1, 2, 16 17 & 18) for a minimum of 30-minutes after study drug administration. Vital signs and AE assessments will be done at 30 minutes (+/- 10 minutes) post-																		
injection. ³ Patients will be randomized to treatment arm 1, 2, or 3 and will follow the corresponding treatment plan.																		

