7. ASSESSMENT OF SAFETY

Safety will be assessed by monitoring adverse events, vital signs, and clinical laboratory measurements. Data from ECG will be included in safety analysis only when all of these measures are available for each subject (baseline and last visit). Adverse events will be monitored from visit 1 (week 0) (post-injection) through visit 33 (week 32) as well as during the 4-week follow up period (visit 34 at week 36). Any serious adverse events whether related or not to study drug will be followed up until resolution.

Study drug, bermekimab, will be administered under close observation in a facility equipped to handle anaphylaxis or injection site reactions. Subjects must be closely monitored at the study site at visits 1, 2, 3, 17, 18 & 19 (for the first three injections) until at least 30 minutes following the administration of the antibody. Vital signs and AE assessments will be done at 30 minutes (+/- 10 minutes) post-injection.

Any grade 3 or greater adverse event or injection site reaction must be reported to the sponsor within 24 hours of learning of the event.

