9.8 TOXICITY MANAGEMENT

Subjects who develop a new infection while undergoing treatment with bermekimab should be monitored closely. Administration of study injections should be interrupted if a subject develops an infection requiring IV anti-infective treatment or if an infection meets the definition of "serious" (refer to Section 9.2 DEFINITION OF SERIOUS ADVERSE EVENT (SAE) for definition). Study medication may be restarted once the physician determines that the infection has been successfully treated. Otherwise prohibited concomitant medications may be given if medically necessitated. Specifically, if a patient develops an intercurrent infection, then topical and/or oral antibiotic usage is permitted. If a patient experiences an intercurrent illness associated with pain for which oral analgesia is required, then otherwise-prohibited oral analgesics are permitted. Topical and/or oral antibiotic usage are not permitted for worsening of HS (except as specified in Section 2.11.2 Antibiotic Rescue Therapy. Prior to use, every attempt should be made to contact the Sponsor's Medical Director for direction on re-introduction of bermekimab therapy after prohibited medication administration.

If the subject must undergo elective surgery, the study injections must be interrupted 2 weeks prior to the surgery. If the subject must undergo emergency surgery, the study injections must be interrupted at the time of the surgery. The injectable study medication can recommence at least 2 weeks after surgery once the physician has examined the surgical site and determined that it has healed and there is no sign of infection.

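### The 30-minute post-injection observation is set by dose in Section 9.7 but by fixed visits elsewhere, and interruptions under Section 9.8 can separate the two

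*Protocol*

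**What the plan says.** **By dose.** Protocol 9.7 presents close monitoring as the mitigation for injection reactions to this drug class. It requires monitoring during the injection and "for at least 30 minutes after the end of the infusion/ injection for the first 3 doses".

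**By visit.** Protocol 5.1 has patients "monitored at the study site at visits 1, 2, 3, 17, 18 & 19 (weeks 0, 1, 2, 16, 17 & 18"), with vital signs and an AE assessment at 30 minutes (plus or minus 10). Footnote 2 of the study calendar gives the same list: "visits 1, 2, 3, 17, 18 & 19 (weeks 0, 1, 2, 16 17 & 18) for a minimum of 30-minutes". The synopsis and Section 3 give the same six weeks.

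**Both at once.** Protocol Section 7 requires monitoring "at visits 1, 2, 3, 17, 18 & 19 (for the first three injections) until at least 30 minutes" after administration. It lists six visits and describes them as three injections.

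**Interruptions.** Protocol 9.8 says that injections should be interrupted for an infection that is serious or needs IV treatment. For elective surgery "the study injections must be interrupted 2 weeks prior to the surgery", and for emergency surgery they stop at the time of surgery. As to restart: "The injectable study medication can recommence at least 2 weeks after surgery once the physician has examined the surgical site". The section does not mention observation at restart.

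**Rescheduling.** SAP 2.2 requires contact with the sponsor over significant scheduling deviations and sets resumption of dosing relative to Week 0.

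**Arm 2.** After loading doses at Weeks 0 and 1, Arm 2 receives "injections of 400 mg bermekimab every other week (q2w) alternating with matching placebo q2w through week 31". Which of Weeks 2 and 3 is active is not stated.

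**Analysis.** SAP 6.1 summarises 30-minute injection-site reactions at Weeks 0, 1 and 2.

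**The concern.** The six listed visits appear to stand in for a dose count. Weeks 0-2 are the first weeks of active drug in Arms 1 and 2, and Weeks 16-18 are the first three active injections in Arm 3. That works only while every injection is given on schedule, and Section 9.8 itself takes injections out of the schedule.

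After such a gap, a site that follows the calendar has no prompt for the 30-minute stay or for the vital-sign and AE check. A site that follows 9.7 would have to count bermekimab doses, which blinded staff cannot do. Sites could therefore act differently on the same facts. The first exposures affected would then lack the timed reaction data that the protocol means to collect.

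**Working it through.** The only computed figure beside the 9.7 rule is the past reaction rate: 27/911 = 2.96%, which rounds to the stated 3.0%. It reproduces, and nothing below depends on it.

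The check is a listing of the schedule. Take each arm's active-dose weeks, remove those withheld under 9.8, take the first three doses actually given, and compare them with the list {0, 1, 2, 16, 17, 18}.

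Assumptions: Week 0 is given in Arms 1 and 2; calendar weeks do not shift after an interruption; surgery falls on a weekly visit S; dosing restarts at the earliest time allowed, S+2. Elective surgery then removes S-2 to S+1 (four weekly injections), and emergency surgery removes S and S+1. The documents fix no length for an infection interruption, so a range is shown.

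**No interruption**
- Arm 1: Weeks 0, 1, 2. All on the list.
- Arm 3: Weeks 16, 17, 18. All on the list.
- Arm 2: Weeks 0, 1, 2 if Week 2 is active, or 0, 1, 3 if Week 3 is. The documents do not settle which.

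**Arm 3, elective surgery**

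| Surgery week | Withheld | First three bermekimab doses | Off the list |
|---|---|---|---|
| 15 | 13-16 | 17, 18, 19 | 1 |
| 16 | 14-17 | 18, 19, 20 | 2 |
| 17 | 15-18 | 19, 20, 21 | 3 |
| 18 | 16-19 | 20, 21, 22 | 3 |
| 19 | 17-20 | 16, 21, 22 | 2 |
| 20 | 18-21 | 16, 17, 22 | 1 |

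The Week 17 row does not depend on how the two-week boundary is read. If the Week 15 injection is given, Weeks 16, 17 and 18 are still withheld and the first three doses are still 19, 20, 21.

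**Arm 3, other interruptions**
- Emergency surgery at Week 16 withholds 16 and 17. Doses fall at 18, 19, 20: two off the list.
- One injection missed for infection at Week 16, 17 or 18: one off the list.
- Three missed from Week 16: doses at 19, 20, 21, all three off the list.

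**Arm 1**
- Elective surgery at Week 3 withholds 1-4. Doses fall at 0, 5, 6: two off the list.
- Elective surgery at Week 4 withholds 2-5. Doses fall at 0, 1, 6: one off the list.
- Emergency surgery at Week 1 withholds 1 and 2. Doses fall at 0, 3, 4: two off the list.

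**Arm 2**
- Elective surgery at Week 3 gives 0, 6, 8 if Week 2 is active, or 0, 5, 7 if it is placebo. Two are off the list either way.

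With Week 0 given, Arms 1 and 2 lose at most two of three. Arm 3 can lose all three.

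**SAP side.** The protocol schedules the 30-minute check at Weeks 0, 1, 2, 16, 17 and 18. The SAP 6.1 summary covers Weeks 0, 1 and 2. Arm 3's first bermekimab injection is at Week 16, so its first active doses lie outside that summary even with full adherence.

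**The case against.** The strongest reply is that an injection off the visit list is not thereby unobserved. Section 7 says, without limiting it to particular visits, that study drug is given under close observation in a facility equipped for anaphylaxis. Section 5.1 lists post-injection AE monitoring at every dosing visit. Section 9.6 asks for prompt reporting of injection-site reactions to the sponsor. Section 9.7 and the Section 7 gloss do not lapse when a visit slips, so a site relying on them would still observe. SAP 2.2 brings the sponsor into significant rescheduling. All of this stands. A reader might infer that early doses are given with no observation at all, and the documents do not support that. What they lack after an interruption is an agreed trigger for the timed 30-minute stay and check.

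A reader might also want a frequency, for instance by assuming a chance that each injection is missed and treating the weeks as independent. The documents give no such rate, and surgical interruptions under 9.8 remove consecutive injections, so that calculation would not describe them.

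A third tempting reading is that every Arm 2 participant receives the third bermekimab dose off the list. That needs Week 3, not Week 2, to be the active week, which is not stated. It also fails if Section 7's count of injections is taken literally: each loading dose is two injections, so Arm 2 has had 2 + 2 = 4 active injections, all at listed visits, by Week 1.

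Finally, the infection wording in 9.8 is advisory; only the surgery wording is mandatory. That is correct, but an advised interruption moves doses just as a required one does.

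**Conclusion.** The contradiction is real and narrow. Section 9.7 counts doses, the other passages list visits, and Section 7 treats the two as the same. Without interruption, Arms 1 and 3 are covered under either rule. An interruption that overlaps Weeks 0-2 in Arms 1 and 2 can leave one or two of the first three bermekimab doses off the list. One that overlaps Weeks 16-18 in Arm 3 can leave one to three off, and elective surgery at Week 17 leaves all three. These results assume that the calendar stays anchored to Week 0 and, for surgery, that dosing restarts at the earliest time allowed.

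How many participants would be affected cannot be derived from the documents. The consequence is inconsistent application of a stated safety measure and gaps in its timed data. The primary efficacy comparison is not at issue.

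The gap in SAP 6.1 is separate and needs no interruption. Reactions recorded as AEs after Arm 3's first bermekimab dose still enter the general AE tables, but the 30-minute summary as written leaves out that arm's first active doses.

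**What to change.** - Reconcile the synopsis, Section 3, the 5.1 note, both sets of calendar footnotes, Section 7 and Section 9.7 with Section 9.8, so that all identify the same injections, including after injections have been missed or withheld. Settle whether the count is of doses or of single injections.
- Use wording that blinded staff can apply to all arms without knowing the allocation.
- Align the 30-minute vital-sign and AE page of the eCRF with the reconciled wording.
- State whether Week 2 or Week 3 is active in Arm 2, where only those who may know the allocation sequence can see it if need be, so that agreement with a dose count can be checked.
- Bring SAP 6.1 into line with the visits at which the protocol schedules the check, so that Arm 3's first active doses are covered or their omission is explained.

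This review does not say which observation rule is right; the sponsor must decide that. The cost is a wording change in several places, one eCRF page and one SAP sentence. The possible downside is a few extra 30-minute stays, depending on how the passages are reconciled.
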